### 13. Participant timeline

- After accepting to be enrolled in this study, all patients will receive proper oral hygiene instructions and will be motivated to stick to these instructions.
- After receiving the treatment, patients will be followed-up for 6 months.

Time point	T0	T1	T2	T3(weekly till T4)	T4(1 month)	T5 (3 months)	T6(6 months)
Enrollment	X						
Eligibility screening	X						
Informed consent	X						
Initial phase (oral hygiene)		X					
Allocation			X				
Intervention			X				
Post-operative care				X	X		
		Assessment					
Radiograph	X			x	X	X	X
Recession depth		X				X	X
%of root coverage							X
Probing depth		X				X	X
Clinical attachment level		X				X	X
Gingival biotype		X				X	X
RES							X
Questionnaire					X		
Post-operative pain				X			

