#### **-Aim of the study**

The aim of this randomized controlled clinical trial with a 6 months follow-up is to evaluate the effectiveness of CAF+SCTG+PRF in the treatment of Miller class I and II recession defects and to compare the outcomes to CAF+SCTG alone.

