**PRF preparation:**

This procedure will be done only if the patient is allocated to group A where PRF will be placed and after the flap in the recession site has been prepared. Just before SCTG harvesting, blood will be taken from the anticubital region with a 24-gauge needle and injected into the 10-mL glass coated collection tube without anti-coagulant then immediately centrifuged at 2700 rpm for 12 minutes with a table centrifuge. The fibrin clot will be collected from the middle part of the tube and packed tightly in 2 sterile saline impregnated gauze in order to obtain a fibrin membrane.

A post-surgery protocol will be implemented emphasizing wound stability and infection control, including 0.12% chlorhexidine rinse twice per day. Gingival sutures will be removed 2 weeks post-surgery. Mechanical plaque control in the surgical area will be reinstated at week 8 following surgery. Patients will be recalled for supragingival scaling and oral hygiene instructions on a monthly basis for the 6-month observation interval.

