#### **12- Outcomes:**

[name] is responsible for measuring all the outcomes and collecting data.

	Outcome name	Measuring Device	Measuring Unit
Primary1ry	Recession depth	William's graduated Periodontal probe	Mm
Secondry2ry	Recession width	William's graduated Periodontal probe	Mm
	Root coverage gain	William's graduated Periodontal probe	Mm
	Probing depth	William's graduated Periodontal probe	Mm
	Clinical attachment level	William's graduated Periodontal probe	Mm
	Gingival biotype	William's graduated Periodontal probe	Mm
	Width of keratinized gingiva	William's graduated Periodontal probe	Mm
	Patient satisfaction	Printed questionnaire Binary (Zuhr et al.2014)	Yes/No
	Root coverage	Score	Categorical

	esthetic score	(Cairo et al. 2009)	
	Post-Operative Pain	Numerical Rating Scale (NRS) (Breivik et al. 2008)	Numerical

The probe is held parallel to the long axis of the tooth. The pressure applied with the probe tip should be between 10-20 grams. Blanching of the gingiva should be avoided.

- Recession depth: from the CEJ to the margin of the gingiva at the midbuccal point of the teeth.
- Recession width: measured horizontally between two borders of the recession
- % of root coverage: (preoperative vertical recession – postoperative vertical recession/preoperative vertical recession) x 100.
- Probing depth: measured from the gingival margin to the base of the pocket probe at the midbuccal point of the teeth.
- Clinical attachment loss: measured from the CEJ to the base of the sulcus at the midbuccal point of the teeth.
- Gingival biotype: under local anesthesia from 3 mm below the gingival margin trans-gingivally piercing tissues horizontally, perpendicular to the long axis of the tooth until it contacts bone.
- Width of keratinized gingiva: from the margin of the gingiva to the mucogingival junction at the midbuccal point of the teeth.
- Patient satisfaction: printed yes/ no questionnaire with 3 questions
- Root coverage esthetic score **(Cairo et al. 2009)**
- Post-Operative Pain: Numerical Rating Scale (NRS) with numbers from 0 to 10 ('no pain' to 'worst pain imaginable') for the first 2 weeks postoperatively. (Breivik et al. 2008)

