**18-Data collection methods****18a-Data collection method:**

The phone numbers and address of the patient included in the study will be recorded from them or extracted from the patient's file which will be available at [name] office , the one responsible for filing system in the Oral Medicine and Periodontology department. The data will be collected by dr [name], whether personal or numerical. They will be stored on excel sheets as an electronic copy and printed hardcopy sheets. The outcome data will be collected at 0, 3 and 6 months. Numerical data will be presented as mean and standard deviation

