### مقياس الألم

اليوم	التاريخ
اليوم (0) يوم العملية	
اليوم (1)	
اليوم (2)	
اليوم (3)	
اليوم (4)	
اليوم (5)	
اليوم (6)	
اليوم (7)	
اليوم (8)	
اليوم (9)	
اليوم (10)	
اليوم (11)	
اليوم (12)	
اليوم (13)	
اليوم (14)	

Filled in by the patient

مقياس رضا المريض بعد اجراء العملية

(1-7)

الاسم:

هل تود ان تجرى لك العملية مرة اخرى ؟

هل تناصح بها للاخرين ؟

الى اى مدى انت راض عن النتائج ؟

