### 3. Root coverage esthetic score

The RES system evaluates five variables 6 months following surgery: gingival margin (GM), marginal tissue contour (MTC), soft tissue texture (STT), mucogingival junction (MGJ) alignment, and gingival color (GC). The clinical esthetic evaluation is performed without magnification. Zero, 3, or 6 points are used for the evaluation of the position of the gingival margin, whereas a score of 0 or 1 point is used for each of the other variables

- GM: -Zero points = failure of root coverage (gingival margin apical or equal to the baseline recession)
  - 3 points = partial root coverage;
  - 6 points = CRC.
- MTC: -Zero points = irregular gingival margin (does not follow the CEJ).
  - 1 point = proper marginal contour/ scalloped gingival margin (follows the CEJ).
- STT: - Zero points = scar formation and/or keloidlike appearance .
  - 1 point = absence of scar or keloid formation.
- MGJ: - Zero points = MGJ not aligned with the MGJ of adjacent teeth.
  - 1 point = MGJ aligned with the MGJ of adjacent teeth.
- GC: -Zero points = color of tissue varies from gingival color at adjacent teeth.
  - 1 point = normal color and integration with the adjacent soft tissues.

Thus, the ideal esthetic score is 10.

Zero points are assigned if the final position of the gingival margin is equal or apical to the previous recession depth (failure of root coverage procedure), irrespective of color, the presence of a scar, MTC, or MGJ. Zero points are also assigned when a partial or total loss of interproximal papilla (black triangle) occurred following the treatment.

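### The schedule places the patient satisfaction questionnaire only at 1 month, so satisfaction with the 6-month result is not clearly captured, and section 18a gives different collection times

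*Combined protocol and SAP*

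**What the plan says.** Section 12 defines the outcome as "Patient satisfaction: printed yes/ no questionnaire with 3 questions". Neither that section nor the outcome table in section 7 says when the form is filled in.

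The only place that gives the form a time is the schedule in section 13. The row "Questionnaire" has one mark, under T4 (1 month), and none under T5 (3 months) or T6 (6 months).

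The form itself is in the Appendix and has three items: whether the patient would have the operation again, whether the patient would recommend it to others, and "الى اى مدى انت راض عن النتائج", which asks to what extent the patient is satisfied with the results.

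The rest of the plan works to a 6-month horizon. The aim begins "The aim of this randomized controlled clinical trial with a 6 months follow-up". The Appendix says of the esthetic score: "The RES system evaluates five variables 6 months following surgery".

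Section 18a states: "The outcome data will be collected at 0, 3 and 6 months".

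**The concern.** A question about satisfaction with the results is most informative when the result has been reached and measured. By its own schedule the trial takes no postoperative recession depth before 3 months, and percentage root coverage and RES only at 6 months. At 1 month the patient is asked to judge a result that the trial has not yet begun to measure.

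This matters because esthetics is among the stated reasons for treatment, and a patient's own request for coverage is one route into the trial (section 10). Satisfaction is the only listed outcome that records the patient's view of what was achieved; the other patient-reported outcome is pain in the first 2 weeks. With the form given once, at 1 month, the report could not set the patient's view of the result beside the measured coverage or the clinician-rated RES from the same visit. It also could not show whether a difference between groups seen at 1 month, or the absence of one, still held at 6 months.

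The two statements on timing also differ, so people working from different sections could collect the form at different times.

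**Working it through.** The plan states no figure for this point that could be reproduced, and nothing here depends on the sample size or on power. The check is a reading of the schedule, a comparison of sections, and two subtractions.

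**Step 1: where the marks fall.** Column positions were counted along each row of the section 13 table. Other rows were read the same way, to make sure that the questionnaire mark had not shifted in the text extraction.

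| Row | Marked at |
|---|---|
| Recession depth | T1, T5 (3 months), T6 (6 months) |
| Percentage root coverage | T6 (6 months) |
| RES | T6 (6 months) |
| Post-operative pain | T3 (weekly until T4) |
| Questionnaire | T4 (1 month) |

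The comparison rows land where other sections lead one to expect. RES is at 6 months, as in the Appendix. Recession depth is at baseline, 3 and 6 months, as in section 7. Pain is in the early weeks, as in section 12. The T4 reading for the questionnaire can therefore be relied on.

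**Step 2: the intervals.**

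- Questionnaire to the final assessment: 6 − 1 = 5 months.
- Questionnaire to the first postoperative recession depth: 3 − 1 = 2 months.

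**Step 3: the two statements on timing.**

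- If the schedule governs, the form is given at 1 month only.
- If section 18a governs, the form is given at 0, 3 and 6 months and not at 1 month. That cannot apply literally, because a form about the operation and its results has no meaning before surgery.
- If section 18a is only a general statement about the clinical measurements, it does not place the form at all. Pain supports this reading: it is collected in the first 2 weeks, which is also outside 0, 3 and 6 months.

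No reading clearly schedules a 6-month questionnaire, and the one item-specific entry leaves that cell blank.

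**Step 4: item by item.** Items 1 and 2 (have it again, recommend it) draw largely on the experience of surgery and recovery, and can be answered usefully at 1 month. Item 3 refers to the results. It is the item for which a 1-month reading and a 6-month horizon do not match.

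**The case against.** The best defence is that an early patient-reported reading is a legitimate choice. Not every secondary outcome has to be read at the last visit, and pain is deliberately confined to the first 2 weeks. The aim sets a 6-month follow-up, but the PICOTS statement and the primary objective attach it to recession depth. The rationale describes platelet rich fibrin as a promoter of early wound healing, which is itself a reason to ask patients early. The questionnaire is attributed to a cited study, and whether its timing follows that source cannot be checked here. All of this stands as a case for keeping the 1-month reading. It does not explain why an item about the results should have no 6-month reading.

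A reader might also infer more than the documents support:

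- **That the whole satisfaction outcome is uninformative for the trial.** Two of the three items remain usable at 1 month. The mismatch is mainly with item 3.
- **That no 6-month satisfaction data will exist, for all 17 patients per group.** Section 18a leaves the timing in conflict rather than plainly absent. The 17 is also an enrolment figure: section 14 raises 14 to 17 to cover losses, so it allows for 17 − 14 = 3 per group and is not the number expected at 6 months.
- **That the 1-month answers are biased because brushing of the site is still withheld.** Section 11a does say "Mechanical plaque control in the surgical area will be reinstated at week 8 following surgery". One month is 365.25 / 12 / 7 = 4.35 weeks, so the form comes 8 − 4.35 = 3.65 weeks earlier. Nothing in the documents links this to how patients rate the result, so no bias is shown.
- **That a passing healing benefit would appear as satisfaction and be gone by 6 months.** This is possible, but the documents give no data on how satisfaction or the gingival margin changes between 1 and 6 months.

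**Conclusion.** The point holds in limited form. As scheduled, satisfaction with the final result, which is mainly item 3, is not captured. The only scheduled answer comes 5 months before percentage root coverage and RES and cannot be compared with them at the same visit. Sections 13 and 18a disagree on when outcome data are collected and must be reconciled.

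The consequence is modest. Satisfaction is one of nine secondary outcomes. Recession depth, the primary outcome, is measured at 6 months and is unaffected, as are root coverage and RES. The case for acting is that the change costs almost nothing and a 6-month answer that was not asked for cannot be recovered later.

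The conclusion assumes that staff follow the item-specific schedule where it differs from the general sentence in section 18a. If they gave the form at 6 months on the strength of section 18a, the data gap would close, but the text would still need correcting. The size of any difference between 1-month and 6-month satisfaction cannot be estimated from the documents.

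**What to change.** - **Section 13:** add a mark for the questionnaire at T6 (6 months).
- **Section 18a:** amend the sentence on collection times so that it agrees with the schedule, naming the questionnaire and its times.
- **Sections 7 and 12:** state that the 6-month reading is the satisfaction-with-results outcome.
- **The 1-month reading:** keep it and report it separately as an early-experience result, where the items on repeating and recommending the surgery are most useful.

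The cost is a short amendment, one extra printed page per patient, and a few minutes at a visit that already takes place. No clinical procedure changes.

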#### **14 - Sample size**

The aim of this study is to evaluate the use of coronally advanced flap and subepithelial connective tissue graft with or without platelet rich fibrin regarding Recession depth. In a previous study by **Keceli et al., 2015** the expected difference in Recession depth decrease from baseline between 2 groups is  $0.45\pm0.38$ mm. Using power 80% and 5% significance level we will need to study 12 in each group to be able to reject the null hypothesis that the population means of the experimental and control groups are equal. This number is to be increased to 14 in each group to correct for non-parametric usage and increased again to 17 to compensate for possible losses during follow up. Sample size calculation was achieved using PS: Power and Sample Size Calculation software Version 3.1.2 (Vanderbilt University, Nashville, Tennessee, USA ).

#### **15- Recruitment strategy:**

- Patients will be selected from the outpatient clinic of the Oral Medicine and Periodontology department, Faculty of Oral and Dental Medicine-Cairo University
- Screening of patients will continue until the target sample is achieved. (Consecutive sampling)
- Identifying and recruiting potential subjects will be achieved through patient database.

#### **16-Allocation**

Patients will be randomly allocated using computer generated randomization ([www.randomizer.org](http://www.randomizer.org)) and will be performed by [name]. The numbers will be allocated to each patient.

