### 10. Eligibility criteria

**i) Inclusion criteria:** Patients eligible for the trial must comply with all of the following:

- 1) Patients 18 years and older
- 2) Buccal recession defects classified as either Miller class I or II gingival recession.
- 3) Clinical indication and/or patient request for recession coverage
- 4) Good oral hygiene

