## **20- Statistical method:**

Data management and statistical analysis will be performed using Statistical Package for Social Sciences (SPSS) vs. 21. Numerical data will be summarized using means and standard deviations or medians and ranges. Data will be explored for normality using Kolmogrov-Smirnov test and Shapiro-Wilk test. Categorical data will be summarized as percentages. Comparisons between two groups and over time will be done by 2 way analysis of variance for repeated measures. If the time factor is not considerable, comparisons between the two groups for normally distributed numeric variables will be done using the Student's t-test while for non-normally distributed numeric variables will be done by Mann-Whitney test. A p-value less than or equal to 0.05 will be considered statistically significant. All tests will be two tailed.

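### Miller class I and II defects are pooled, but class is neither a stratum in the allocation nor a term in the analysis, so a chance class difference between arms stays in the primary comparison.

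*Combined protocol and SAP*

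**What the plan says.** Section 10 of the combined protocol and SAP admits "Buccal recession defects classified as either Miller class I or II gingival recession", with no quota for either class; classes III and IV are excluded.

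Section 16 states "Patients will be randomly allocated using computer generated randomization". Sections 16a and 16b add that the numbers go into opaque sealed envelopes, that the participant draws one, and that an independent person does the randomisation. They give no ratio, block, stratum or minimisation factor, and do not say how the envelope set is made up.

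Section 14 sets the size: "we will need to study 12 in each group", then "This number is to be increased to 14 in each group to correct for non-parametric usage", then "increased again to 17 to compensate for possible losses during follow up". That is 34 patients.

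Section 20 gives the analysis: "Comparisons between two groups and over time will be done by 2 way analysis of variance for repeated measures". If time is judged unimportant, it falls back to a t-test or a Mann-Whitney test between the two groups. Miller class appears in no model, subgroup or sensitivity analysis.

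**The concern.** A baseline feature can be balanced by the allocation, adjusted for in the analysis, or left to chance. The plan leaves Miller class to chance, although class has to be established at screening to decide eligibility and so is known before allocation.

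With 14 to 17 patients per arm, a noticeable excess of one class in one arm is not rare. If class is related to how much the recession shrinks, that excess moves the estimated effect of platelet-rich fibrin, and nothing in section 20 takes it out. Readers of the result would then have to guess how much of the difference came from class. Even without imbalance, variation between classes stays in the error term and widens the confidence interval.

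**Working it through.** **Inputs from the documents.** Section 14: difference 0.45 mm; 0.38 mm, read as a standard deviation; "Using power 80% and 5% significance level"; 17 per group. Section 20: "All tests will be two tailed".

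**Assumptions (not in the documents).** Class II share of 30-50%, represented by 10, 14 or 17 of 34 patients. Class effect on the decrease in recession depth of 0.2-0.5 mm.

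**1. The plan's own figure.** n per arm = 2 × [0.38 × (1.960 + 0.842) / 0.45]² = 11.19, rounded up to 12. This matches. The 14 is consistent with 12 × 1.15 = 13.8, and the 17 with 14 / 0.85 = 16.5 or 14 × 1.2 = 16.8; section 14 does not state these factors.

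**2. How often the classes are unbalanced.** With arms fixed at 17:17 and M class II patients, the number X in one arm is hypergeometric (34, M, 17). The class II shares differ by |2X − M| / 17. For simple 1:1 allocation, the same calculation is averaged over Binomial(34, 0.5) arm sizes.

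| Class II patients of 34 | 20 points or more, fixed 17:17 | 20 points or more, simple | 30 points or more, fixed 17:17 | 30 points or more, simple |
|---|---|---|---|---|
| 10 | 25.9% | 22.2% | 5.7% | 6.5% |
| 14 | 29.6% | 26.0% | 8.0% | 8.5% |
| 17 | 16.9% | 24.3% | 3.8% | 7.6% |

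So a difference of 20 points or more occurs in about 17-30% of allocations, and one of 30 points or more in about 4-9%. With only 7 class II patients, the 20-point figures fall to 8.5% (fixed) and 17.9% (simple).

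**3. Shift in the unadjusted contrast** = imbalance × class effect.
- 20 points: 0.20 × 0.2 = 0.04 mm to 0.20 × 0.5 = 0.10 mm, or 9-22% of 0.45 mm.
- 30 points: 0.30 × 0.2 = 0.06 mm to 0.30 × 0.5 = 0.15 mm, or 13-33% of 0.45 mm.

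**4. Scale.** The standard error of the contrast is 0.38 × √(2/14) = 0.144 mm at 14 per arm, and 0.38 × √(2/17) = 0.130 mm at 17. A shift of 0.04-0.10 mm is 0.3-0.7 of the standard error at 14 per arm.

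**5. What adjustment could save.** If 0.38 mm is the total SD in the enrolled mix, class accounts for g²p(1 − p) of the variance 0.38² = 0.1444, where g is the class effect and p the class II share.
- g = 0.2: 0.0084 (p = 0.3) to 0.0100 (p = 0.5), or 6-7%. The residual SD falls to √(0.1444 − 0.0084) = 0.369 or √(0.1444 − 0.0100) = 0.367, a gain of 3-4%.
- g = 0.5: 0.0525 to 0.0625, or 36-43%. The residual SD falls to 0.303 or 0.286, a gain of 20-25%.

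These gains ignore the lost degree of freedom and the slight inflation that imbalance itself causes.

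**6. Arm sizes.** Noncentral-t power at the plan's inputs with 28 evaluable patients is 85.4% at 14:14 and 82.4% at 18:10.

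**The case against.** **Chance imbalance is ordinary sampling error.** Randomisation makes the comparison unbiased on average, and the unadjusted test keeps its 5% level. This stands and limits the point to precision and interpretability.

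**The class effect is unknown.** Excluding classes III and IV does not show that I and II respond differently. Recession depth is also measured at baseline, so the group-by-time comparison already allows for different starting depths. This stands in part: the upper assumption of 0.5 mm would make class account for 36-43% of the outcome variance, which is a lot. Adjusting for starting depth, however, does not adjust for a different response to surgery by class.

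**An unstratified list is an accepted choice in a single-centre trial of 34.** True, but it makes adjustment in the analysis more useful.

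**A stronger reading.** Because no restriction is named, a reader might infer that allocation is unrestricted and that arm sizes are left to chance. The documents do not support this. They do not state the type of sequence, they plan 17 per group, and a prepared set of 17 + 17 envelopes would deliver exactly that. Under simple allocation 17:17 would occur in only 13.6% of cases, but even an 18:10 split costs about 3 points of power (step 6) and stays above 80%.

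**Conclusion.** The point holds for Miller class. Class is pooled, not stratified and not in the model, so a chance difference between arms stays in the primary result. The likely size is modest: the 20-point shift stays below one standard error across the assumed ranges. It would be wrong to attach the 17-30% chance to a shift of a third of the planned effect, because that shift needs a 30-point imbalance (about 4-9%) together with the largest assumed class effect.

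The class mix and the class effect are assumptions throughout. What is certain is the omission and that correcting it is cheap. On arm sizes, the finding is only that the ratio and type of sequence should be stated. This is a worthwhile improvement, not a flaw in validity.

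**What to change.** **Section 20.** Add Miller class (I/II) to the primary model as a between-patient factor with its interaction with time. A class main effect alone would adjust only the average level over visits, not the change. For the 6-month contrast, the equivalent is a linear model of the change in recession depth on arm and class. Use this adjusted model in place of the unadjusted t-test for the primary outcome. If normality fails, replace the Mann-Whitney test with a class-stratified rank test (van Elteren).

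**Data sheet.** List Miller class as a recorded baseline item. It is needed for eligibility, but the outcome list and participant timeline do not name it.

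**Section 16, whatever the stage of recruitment.** State the ratio, the type of sequence and how the envelope set is made up.

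**Section 16, only if recruitment has not begun.** Generate the list 1:1 in permuted blocks of randomly varying, undisclosed size, separately for class I and class II. Issue each class's envelopes in order; the participant would no longer draw freely.

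**Cost.** One degree of freedom per contrast, two envelope sets and a few lines of text. The unblinded operator could sometimes guess the end of a block, which varying block sizes limit. The sample size does not change: with blocks of at most 4, the arms stay within 19:15, with power of 91.4% against 91.7% at 17:17. If class is weakly related to the change in recession depth, the gain is small (3-4% in the standard error at 0.2 mm).
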